### Hematology, Clinical Chemistry, and Urinalysis

Hematology

Complete blood count with platelet count and standard indices will be obtained.

Chemistry

Sodium, potassium, chloride, carbon dioxide (CO2), albumin, total protein, glucose, blood urea nitrogen (BUN), creatinine, uric acid, AST, ALT, gamma-glutamyltranspeptidase (GGT), creatine phosphokinase (CPK), alkaline phosphatase, total bilirubin, direct bilirubin, lactate dehydrogenase (LDH), calcium, and phosphorus.

• Coagulation Profile

Prothrombin time (PT) or international normalized ratio (INR), and partial thromboplastin time (PTT), also referred to as activated partial thromboplastin time (aPTT).

Urinalysis

pH, glucose, protein, ketones, bilirubin, blood, urobilinogen, specific gravity, nitrite, and leukocytes by dipstick analysis or machine urinalysis. Urine microscopic examination will be performed if positive findings on dipsticks warrant further examination.

### 11.21. Anti-drug Antibody Samples

Blood samples for measurement of anti-drug antibodies (ADA) will be collected according to the SOA (Table 3). Any patient with a positive titer will be followed until resolution.

## 11.24. Injection Site Inspection

Injection sites will be carefully inspected, evaluated, and scored according to the SOA (Table 3). The injection site evaluation will include identification and measurement of areas of erythema, edema, and induration, as well as the presence of localized pain, tenderness, and itching. A sample injection site evaluation form is included in Appendix A.

In addition, unscheduled evaluations may also be recorded as warranted by clinical conditions.

### 11.25. Telephone Call

The site will call a patient's home on Day 15 to assess AEs and ensure the patient escalated to the appropriate dose depending on age, as outlined in the SOA (Table 3).

### 11.26. Study Drug Administration

Study drug will be administered daily as outlined in the SOA (Table 3).

### 11.27. Dispensing/Return of Study Drug

Study drug will be dispensed as outlined in the SOA (Table 3) and Section 9.5. Any unused drug will be returned to the clinic site and the Sponsor as described in Section 9.6.

#### 11.28. Adverse Event Assessment

Each patient must be carefully monitored for the development of any AEs throughout the study from Screening through the Final Study Visit. This information should be obtained in the form of non-leading questions (e.g., "How are you feeling?"), and from signs and symptoms detected during each examination, from laboratory evaluation, observations of study personnel, and spontaneous reports from patients.

All AEs, including injection site reactions and potential systemic reactions, will be graded using the National Cancer Institute Common Terminology Criteria for Adverse Events (NCI CTCAE) grading system.

Complete details on AE monitoring are provided in Section 12.

## 11.29. Concomitant Medication(s) Review

A review of concomitant medications will be conducted during the Screening Period and at every study visit. Any medications taken by study patients will be recorded in source documents and on the appropriate eCRF.

#### 12. ADVERSE EVENTS

Monitoring of AEs will be conducted throughout the study. AEs will be recorded in the CRFs from Screening through the Final Study Visit. AEs that occur after the start of study drug administration will be considered TEAEs. SAEs will be recorded through the Final Study Visit (EOS Visit 7, or Treatment Discontinuation). All AEs should be monitored until they are resolved or are clearly determined to be due to a patient's stable or chronic condition or intercurrent illness(es).

### 12.1. Definitions, Documentation, and Reporting

An adverse event (AE) is any untoward medical occurrence associated with the use of a drug in humans, whether or not considered drug-related. An AE (also referred to as an adverse experience) can be any unfavorable and unintended sign (e.g., an abnormal laboratory finding), symptom, or disease temporally associated with the use of a drug, without any judgment about causality. An AE can arise from any use of the drug (e.g., off-label use, use in combination with another drug) and from any route of administration, formulation, or dose, including an overdose.

An AE is considered serious (SAE) if, in the view of either the Investigator or Sponsor, it results in any of the following outcomes:

- Death.
- Life-threatening. Life-threatening means that the patient was at immediate risk of death from the reaction as it occurred, i.e., it does not include a reaction which hypothetically might have caused death had it occurred in a more severe form.
- In-patient hospitalization or prolongation of existing hospitalization. Hospitalization admissions and/or surgical operations scheduled to occur during the study period, but planned prior to study entry, are not considered AEs if the illness or disease existed before the patient was enrolled in the study, provided that it did not deteriorate in an unexpected manner during the study (e.g., surgery performed earlier than planned).
- A persistent or significant incapacity or substantial disruption of the ability to conduct normal life functions.
- Congenital anomaly/birth defect.
- Important medical event. An important medical event is an event that may not result in death, be life-threatening, or require hospitalization but may be considered an SAE when, based upon appropriate medical judgment, it may jeopardize the patient or patient and may require medical or surgical intervention to prevent one of the outcomes listed in the definitions for SAEs. Examples of such medical events include allergic bronchospasm requiring intensive treatment in an emergency room or at home, blood dyscrasias or convulsions that do not result in in-patient hospitalization, or the development of drug dependency or drug abuse.

### 12.2. Procedures for AE and SAE Reporting

Each patient must be carefully monitored for the development of any AEs. This information should be obtained in the form of non-leading questions (e.g., "How are you feeling?") and from signs and symptoms detected during each examination, observations of study personnel, and spontaneous reports from patients.

All AEs (serious and non-serious) spontaneously reported by the patient and/or in response to an open question from study personnel or revealed by observation, physical examination, or other diagnostic procedures will be recorded on the appropriate CRF. Any clinically relevant deterioration in laboratory assessments or other clinical findings is considered an AE and must be recorded on the appropriate CRF. When possible, signs and symptoms indicating a common underlying pathology should be noted as one comprehensive event.

All SAEs that occur during the study must be reported by the Investigator **within 24 hours** from the point in time when the Investigator becomes aware of the SAE. All SAEs must be reported whether or not considered causally related to the study drug. SAE forms will be completed and the information collected will include patient number, a narrative description of the event, and an assessment by the Investigator as to the severity of the event and relatedness to study drug. Follow-up information on the SAE may be requested by the Sponsor or its designee.

- All SAE correspondence should be addressed to
- Email: [contact]

If there are serious, unexpected adverse drug reactions associated with the use of the study drug, Rhythm or designee will notify the appropriate regulatory agency(ies), Ethics Committees (EC), and all participating Investigators on an expedited basis. It is the responsibility of the Investigator to promptly notify the Institutional Review Board (IRB)/Independent Ethics Committee (IEC) of all unexpected serious adverse drug reactions involving risk to human patients. An unexpected event is one that is not reported in the IB (see IB Section 6.1.3, Reference Safety Information).

For both serious and non-serious AEs, the Investigator must determine both the intensity of the event and the relationship of the event to study drug administration. Only those injection site reactions considered clinically significant by the Investigator will be recorded as AEs.

### 12.2.1. Assessment of Severity

Intensity of all AEs including clinically significant treatment-emergent laboratory abnormalities, injection site reactions, and potential systemic reactions will be graded per the CTCAE Version 4.03. The CTCAE grade refers to the severity of the AE and ranges from Grade 1 (mild AE), Grade 2 (moderate AE), Grade 3 (severe AE), and Grade 4 (life-threatening or disabling AE) to Grade 5 (death related to AE).

AEs not listed by the CTCAE will be graded as follows:

- Mild: discomfort noticed but no disruption of normal daily activity.
- Moderate: discomfort sufficient to reduce or affect daily activity.
- Severe: inability to work or perform normal daily activity.
- Life threatening: represents an immediate threat to life.

**Relationship** to study drug administration will be determined by the Investigator according to the following criteria:

- **None:** No relationship between the event and the administration of study drug. The event is related to other etiologies, such as concomitant medications or patient's clinical state.
- Unlikely: The current state of knowledge indicates that a relationship to study drug is unlikely, the temporal relationship is such that study drug would not have had any reasonable association with the observed event, or another reasonable explanation for the event (e.g., a pre-existing clinical condition or other concomitant treatment) is more likely.
- **Possible:** A reaction that follows a plausible temporal sequence from administration of the study drug and follows a known response pattern to the suspected study drug. The reaction might have been produced by the patient's clinical state or other modes of therapy administered to the patient.
- **Probable:** A reaction that follows a plausible temporal sequence from administration of the study drug and follows a known response pattern to the suspected study drug. The reaction cannot be reasonably explained by the known characteristics of the patient's clinical state or other modes of therapy administered to the patient.

For the purpose of safety analyses, all AEs that are classified as possible or probable will be considered treatment-related events.

#### 12.2.2. Adverse Events and Risks

Overall, setmelanotide has been generally well-tolerated in previous studies. Drug-Related TEAEs (for which the AE was assessed as possibly or probably related to study drug by the Investigator) were reported. Because very few studies have been done using setmelanotide, there may be other unknown side effects. The Primary Investigators (or a covering clinician) will be available at all times to study participants in the event of a clinical emergency; both this availability and how to reach the Investigators in an emergency will be clearly communicated orally and in writing to study participants. All study interventions will be provided free of cost.

Please refer to the current IB for a comprehensive summary of the AEs reported to date.

### 12.2.3. Monitoring of Adverse Events and Period of Observation

AEs will be recorded on the CRFs starting from Screening up to and including the Final Study Visit. SAEs and deaths will be recorded on the CRFs starting from the time the informed consent form is

signed and continuing through the Final Study Visit. All AEs should be monitored until they are resolved or are clearly determined to be due to a patient's stable or chronic condition or intercurrent illness(es).

Any SAE that occurs at any time after completion of the study, and which the Investigator considers to be related to study drug, must be reported to Rhythm or its designee.

### 12.2.4. Guidelines for Additional Monitoring and Suspension of Dosing for a Patient

Patients will be monitored carefully during the treatment period during on-site clinic visits and periodic telephone calls made to the patients by the study staff. In the event a patient is withdrawn from treatment due to an AE, the patient should be encouraged to complete the final study/early termination visit in order to monitor the event to resolution and obtain additional protocol-defined safety assessments.

#### Depression or Suicidality

A patient should be referred to an MHP if he/she has:

- A PHQ-9 score  $\geq 10$ .
- Any suicidal behavior.
- Any suicidal ideation of type 4 or 5 on the C-SSRS.

A referral to an MHP should also be made if, in the opinion of the Investigator, it is necessary for the safety of the patient. If a patient's psychiatric disorder can be adequately treated with psychoand/or pharmacotherapy, then the patient, at the discretion of the MHP, should be continued in the trial.

Any elevation in PHQ-9 or C-SSRS score should be evaluated to determine whether it meets the criteria for reporting as an AE.

#### 13. DATA ANALYSIS/STATISTICAL PROCEDURES

This section describes the plans for analysis. Details of the statistical plan will be provided in a complete SAP. Any additional analyses and specific conventions for analysis will be described in the SAP and Clinical Study Report.

### **13.1.** Sample Size Estimation

The objective of this study is to demonstrate statistically significant and clinically meaningful weight loss in patients with various rare genetic forms of obesity after ~3 months of treatment. The primary endpoint is defined as the proportion of patients in each subgroup of RGDO who achieve at least 5% body weight reduction from baseline, at ~3 months treatment with setmelanotide. It is estimated that at least 5 patients with each rare genetic disorder of obesity will be recruited.

Given the rarity of this disorder, estimated power for expected weight change efficacy will not be provided, but efficacy will be only summarized.

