#### **Number of Patients (planned):**

It is expected that approximately 150 patients will be included in this protocol across multiple subgroups. Since the subgroups in this study are all rare, it is expected that the size of each subgroup will range from 1-15 patients.

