#### Statistical considerations:

The objective of this study is to demonstrate clinically meaningful weight loss in patients with various rare genetic forms of obesity after a stable therapeutic dose period, which is expected to be  $\sim$ 3 months of treatment in most subjects. The primary endpoint is defined as the proportion of patients in each subgroup of rare genetic disorders of obesity (RGDO) who achieve at least 5% body weight reduction from baseline, at  $\sim$ 3 months of treatment with setmelanotide.

The study is exploratory in nature and the sample size of the study for each cohort is driven by clinical considerations. The total number of patients enrolled per subtype with specific genetic obesity mutations may be increased or decreased, depending upon the total number of affected patients identified.

These many rare genetic disorders are grouped together into one protocol for administrative reasons, and otherwise would have been studied in separate protocols. Hence, each rare genetic disorder will be treated as a separate population for any statistical analysis, and therefore no multiplicity adjustments will be planned in this early, proof-of-concept study.

Given the rarity of these disorders, estimated power for expected weight change efficacy will not be provided, but efficacy will be only summarized.

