### 13.2. Hypotheses

Setmelanotide leads to a clinically relevant reduction of percent body weight after ~3 months of treatment in each population of patients with rare genetic disorders of obesity (each population analyzed separately). No formal statistical hypothesis will be tested, given the exploratory nature of the study.

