3. GENERAL STATISTICAL METHODS

3.1. Sample Size Justification

It is estimated that at least 5 patients within each subgroup of RGDO will be recruited. Given the rarity of these disorders, the sample size is not driven by statistical considerations, but primarily driven by clinical considerations. Therefore, estimated power for expected weight change will not be provided, and efficacy will be only summarized. P-values and confidence intervals may be provided wherever is appropriate, but these should be considered for estimation and clinical scrutiny purpose, instead of formal statistical hypothesis testing purpose.

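### Do the two forecasts of subgroup size, and the mention of statistical significance in Protocol 13.1, call for a correction?

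*Protocol*

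**What the plan says.** **Size.** Protocol Section 13.1 states: "It is estimated that at least 5 patients with each rare genetic disorder of obesity will be recruited". SAP Section 3.1 has almost the same sentence: "It is estimated that at least 5 patients within each subgroup of RGDO will be recruited". The synopsis (Number of Patients) and Section 8.1 say instead that "it is expected that the size of each subgroup will range from 1-15 patients", within a total of about 150. The synopsis (Statistical considerations) adds that the number per subtype "may be increased or decreased, depending upon the total number of affected patients identified", and that the size of each cohort rests on clinical considerations. SAP 3.1 gives the same basis.

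**Aim.** Section 13.1 opens: "The objective of this study is to demonstrate statistically significant and clinically meaningful weight loss". The matching sentence in the synopsis reads: "The objective of this study is to demonstrate clinically meaningful weight loss in patients with various rare genetic forms of obesity". The next paragraph of Section 13.1 says that "estimated power for expected weight change efficacy will not be provided, but efficacy will be only summarized". Section 13.2 says: "No formal statistical hypothesis will be tested, given the exploratory nature of the study". Section 13.4 plans a one-sided comparison with baseline at 0.05, and the same paragraph ends by calling every p-value and interval exploratory. SAP 3.1 permits p-values for estimation and clinical scrutiny, not for formal testing. SAP 3.7 describes the interpretation as descriptive.

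**The concern.** Results are read disorder by disorder, and the sample size section is where a reader looks for the planned size and purpose. Two things there look wrong.

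First, a subgroup of 1 to 4 patients is expected by the synopsis and Section 8.1 but falls below the estimate in Section 13.1 and SAP 3.1. Someone planning recruitment, or judging afterwards whether a cohort was complete, might take 5 as a minimum.

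Second, an aim of demonstrating statistical significance normally implies a test, a null value, power and an error rate. The plan gives no power and no null value. If a small p-value in one of many subgroups were later presented as the trial meeting its objective, the first sentence of Section 13.1 could be cited in support.

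**Working it through.** **1. Can any stated size be reproduced?** No. The documents give no null response rate, assumed response rate, standard deviation or power, so neither 5, nor 1 to 15, nor 150 comes from a formula. There is no calculation to be wrong.

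**2. Where the forecasts differ.** At least 5 and 1 to 15 agree on 5 to 15 and differ only on 1 to 4. The total does not decide between them. If the ten lettered genotype categories in Inclusion Criterion 1 are taken as the subgroups (an assumption):

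- at least 5 each: 10 × 5 = 50 or more;
- 1 to 15 each: 10 × 1 = 10 up to 10 × 15 = 150.

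Both are compatible with about 150.

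**3. Does any rule use 5 as a minimum?**

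| Place | Number used |
|---|---|
| Protocol 13.3 (when a population is analysed) | 2 or more completers |
| Protocol 13.5 (timing of analysis) | about 2 to 3 completers |
| Protocol 7.4 and SAP 1.3.3 (possible closure of a population) | at least two, possibly up to five |
| SAP 3.12 (data cuts) | pre-specified number, may depend on prevalence |
| SAP 2.1 and 4.3.1 (analysis sets, primary analysis) | no minimum |

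None requires 5. Most of them already provide for fewer.

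**4. Does the forecast enter an estimate?** The primary result is x responders out of n with a two-sided 90% Clopper-Pearson interval (SAP 4.3.1), where n is the number actually in the analysis. With x = 0 the upper limit solves (1 − p)^n = 0.05, so p = 1 − 0.05^(1/n):

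- n = 1: 0.950
- n = 2: 0.776
- n = 3: 0.632
- n = 4: 0.527
- n = 5: 0.451
- n = 15: 0.181

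Small subgroups give very wide intervals, but the width depends on the n observed. Rewording a forecast changes none of these limits.

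**5. Does the significance wording enter a decision?** The primary proportion has no null rate, so the planned analysis cannot declare it significant. The only test is the exploratory comparison with baseline in Section 13.4, whose method is not named. As an illustration, the smallest one-sided p-value of an exact sign test is 0.5^n: 0.0625 at n = 4 and 0.03125 at n = 5. That test could not reach 0.05 below 5 patients, though a paired t-test has no such floor from 2 patients upward. In either case no primary conclusion, power claim or error rate is tied to the p-value.

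**The case for a change.** The strongest case for correcting the text is that two forecasts of one quantity should agree, that the smallest subgroups carry the least information, and that the fix costs only a few words. SAP precedence (SAP 1.1.1) does not settle the size, because SAP 3.1 repeats the estimate of 5 without mentioning 1 to 15. The one-sided test at 0.05 in Section 13.4 also partly echoes the significance wording, so that wording is not wholly isolated.

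All of this is true as description, and tidying the sentences at a later amendment would do no harm. What does not stand is any consequence. A reader who takes 5 as a forecast and a reader who takes 1 to 15 carry out the same analyses at the same times. On the aim, the SAP does settle the reading: its primary objective is exploratory, it does not repeat the significance aim, and it states what p-values are for. Adding an exploratory label to the test sentence in Section 13.4 would repeat one already in that paragraph.

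A separate loose end lies nearby. The closure example in Protocol 7.4 and SAP 1.3.3 mentions a threshold for entering extensions. The documents describe such a threshold only for patients enrolled before Amendment 9 (SAP 1.3.1), and the current design states no weight-loss condition for the extension study. Those passages must be reconciled on their own account. The example is a parenthesis in a discretionary list, and neither the size nor the aim depends on it.

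**Conclusion.** The inconsistencies are real but editorial. The dispute over size covers subgroups of 1 to 4 patients and lies between two soft expectations, while the operative rules already work from 2 patients upward. The significance wording is a slip in one sentence, contradicted in the next paragraph and overridden by Section 13.2 and the SAP. The effect on any estimate, interval, analysis time or planned conclusion is zero, so no change to the plan is called for.

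This rests on two assumptions: that disorder in Section 13.1 and subgroup elsewhere mean the same unit, as SAP 3.1 implies, and that no rule outside these two documents uses 5 as a minimum. It also relies on the report keeping to the plan's own label and presenting any p-value as exploratory.

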### 13.2. Hypotheses

Setmelanotide leads to a clinically relevant reduction of percent body weight after ~3 months of treatment in each population of patients with rare genetic disorders of obesity (each population analyzed separately). No formal statistical hypothesis will be tested, given the exploratory nature of the study.

